## STUDY SUMMARY

Study Title	Patient and staff experience of ambulatory emergency care on the Surgical Admissions Unit (SAU)
Internal ref. no. (or short title)	SAU Interview Study
Study Design	Qualitative semi-structured interviews of patient and staff experience
Study Participants	
 
General surgical patients who have received ambulatory emergency care at the surgical assessment unit.
 
Staff involved in the care of these patients.
 

Planned Size of Sample (if applicable)	20 patients, 12-15 staff members: consultants, junior doctors, senior nurses and junior ward staff who provide care to patients undergoing ambulatory care
Follow up duration (if applicable)	N/A
Planned Study Period	September 2018 – September 2019
Research Question/Aim(s)	What are patients' experience of being managed in an ambulatory manner when they are referred to emergency general surgery? What are the opinions and attitudes of staff towards ambulatory emergency care in general surgery? What barriers would exist to expanding this service?

## ROLE OF STUDY SPONSOR

The sponsor is University of Exeter as this research is being undertaken as part of a Masters by Research degree thesis. The sponsor is and has been involved in all stages of the study in particular the design and will oversee the conduct of the study. The research thesis containing the results of the study will be freely available publicly from the sponsor. The sponsor controls the final decision for all aspects of the study.

## ROLES AND RESPONSIBILITIES OF STUDY MANAGEMENT COMMITTEES/GROUPS & INDIVIDUALS

### Study Steering Groups

#### Patient and public involvement group

The overall design of this study and participant and potential participant information sheets and study literature has been discussed with members of the Royal Devon and Exeter hospital volunteer PPI group. Individuals that responded to a request for help with this research were consulted and changes were made to study documents including the introduction of a more detailed study information sheet as a result. Any changes made to the study as a result of e.g. low recruitment will be discussed with those volunteers.

## **PROTOCOL CONTRIBUTORS**

[figure not shown]
As described previously the sponsor is and has been involved in all stages of the study in particular the design and will oversee the conduct of the study with support from the educational supervisors. The research thesis containing the results of the study will be freely available publicly from the sponsor organisation the University of Exeter. The sponsor controls the final decision for all aspects of the study.

Data collection, data analysis and writing of the manuscript will be undertaken by [name] with input from [name], [name] and [name] as educational supervisors. Corrections to the manuscript may be suggested by the sponsor in their role.

[figure not shown]
As described previously individuals from the Royal Devon and Exeter volunteer PPI group have been involved in the design of the study, in particular the layout and wording of the information sheets. These are a mix of members of the public and previous service users.

**KEY WORDS:** Emergency general surgery  
Ambulatory care  
Patient experience

## STUDY FLOW CHART FOR PATIENT INTERVIEWS

**STUDY FLOW CHART FOR STAFF INTERVIEWS**

## STUDY PROTOCOL

Patient **and staff** experience of ambulatory emergency care on the Surgical Admissions Unit (SAU)

### 1 BACKGROUND

Abdominal pain is a common reason for people to attend hospital as an emergency. It makes up a considerable proportion of the patients being admitted under the care of general surgeons. Other common reasons for people attending include infections such as abscesses and problems following previous surgery.

A Surgical Assessment Unit (SAU) is an ambulatory area with a waiting room and assessment cubicles. It is staffed by a triage nurse or healthcare assistant and doctors from the surgical team. Patients can be assessed and have investigations including blood tests and radiology procedures including x-rays, ultrasound and CT. After assessment they are either admitted to the ward, discharged home or have their care continued in an ambulatory manner returning in the next few days for further or repeat assessment.

Previously patients were either discharged or admitted for observation, investigation and treatment such as intravenous antibiotics. Many of these patients could be managed safely in a "day case" manner. This pathway allows for re-attendance should it be required.

Emergency ambulatory care is well-established in medicine for conditions such as suspected deep vein thrombosis (DVT) and transient ischaemic attack (TIA) but has not yet been widely adopted in surgery.[1] There is uncertainty surrounding the best way of looking after these patients as the diagnosis is often uncertain and it can be difficult to judge which patients require admission.

Pilot studies have shown that up to 30% of emergency general surgical patients could be managed in this way.[2] These studies also report a high patient satisfaction score but do not inform us what works, why and for whom. These would be important considerations for organisations looking to expand their emergency general surgical ambulatory service.

This study aims to expand upon previous work in this area[3] by conducting semi-structured interviews with patients who have experienced emergency general surgical ambulatory care **and the staff who deliver this care.** We hope to identify themes that influence patient experience of emergency ambulatory care and whether this might vary depending on patient factors such as age, social support/responsibilities and attending condition.

**The attitudes and experience of staff who deliver this care will help to understand better some aspects of patient experience and also the way in which ambulatory emergency care has been implemented. We are interested in speaking to staff who are the "decision-makers" for selecting patients for ambulatory care (senior doctors and nurses) and also those who deliver this care (junior doctors and ward support staff including junior nurses, health care assistants, ward receptionists). We are interested in staff perception of patient experience and their attitudes towards the implementation and possible expansion of emergency care.**

The topic guide for the staff interviews have been informed by the Consolidated Framework for Implementation Research (CFIR).[4] This will bring a structured approach to understanding the way in which ambulatory emergency care has been implemented in this department.

## 2 RATIONALE

Emergency ambulatory general surgical care is a new area that is set to expand in the next few years.[1] There will be economic implications to this expansion. Reduction in inpatient stays will reduce healthcare costs but pilot studies have used additional resources such as a separate consultant allocated to the assessment unit and dedicated imaging slots.

Patient experience is an important factor in the quality of the care delivered and will influence how people interact and engage with the service. Within this study we are interested in discovering what factors in the delivery of this care are important for the patient experience, and how this varies amongst patients. This will allow individual clinicians to make better-informed decisions about which patients may not be suitable for ambulatory care, or may need support to enable it to be delivered in a way that works for them. It will also inform organisations looking to expand their ambulatory services about which components of the service are important from a perspective of patient experience.

Our literature review within this field identified that the experiences and attitudes of staff delivering this care may have an effect upon the success of any change in the delivery of this type of care. Examining this in further detail was initially beyond the scope of this study due to time constraints but there has arisen opportunity to devote more time to this project with the expansion of the researcher's degree from MbyRes to MD. We therefore decided to expand our study to include interviews with staff to explore the rationale for their attitudes to this type of care.

We are not gathering data on clinical outcomes or undertaking an economic evaluation. These are also important factors to consider when expanding an ambulatory service but are outside the scope of this study methodology.

## 3 THEORETICAL FRAMEWORK

Data will be analysed using the method of thematic analysis. We have chosen this method because we are interested in individual themes that are important influences on the patient experience. These themes may be quite separate from one another and not related to an encompassing theory, which suits this method of analysis as opposed to e.g. a grounded theory method.[5]

## 4 RESEARCH QUESTION/AIM(S)

To explore general surgical patients' experiences of being managed in an ambulatory manner in the context of a surgical assessment unit (SAU).

To explore staff experience and attitudes of emergency ambulatory care in general surgery. The staff groups of interest are: senior doctors (consultants), senior nurses, junior doctors (all grades) and other ward staff including junior nurses, healthcare assistants and ward receptionists.

#### 4.1 Objectives

To establish why this method of care works better for some people than for others.

**To establish staff's beliefs about ambulatory care and its suitability for different patients.**

**To identify possible barriers to expansion of this method of care.**

#### 4.2 Outcome

To identify which groups of patients are most likely to be able to engage well with this method of care and for whom it would not be appropriate or may need more support. To identify parts of the process specific to ambulatory care that most affects patient experience.

**To understand better staff's beliefs and experience about ambulatory care and how that impacts the way that they deliver this care.**

### 5 STUDY DESIGN and METHODS of DATA COLLECTION AND DATA ANALYSIS

This is a qualitative study of patient experience. Data will be collected by semi-structured telephone interviews **(patients) and face-to-face or telephone interviews (staff).**

#### Interviews with patients

Participants will be recruited to the study by the clinical team by means of short verbal explanation and the provision of an information sheet. Potential participants will give their contact details to be passed to the study team or will make contact themselves at a later stage. They will then be contacted by the study team and given further information over the telephone. Those wishing to proceed will have arrangements made for a telephone interview. A recording of consent will be made prior to the start of the interview and will be stored as a separate audio file.

The interview schedule has been drawn up based on areas that have emerged from work in the past using patient diaries.[3] The PPI work done has included review of these questions for acceptability and ease of understanding and minor changes have been made to the wording of questions as a result. The prompts used are mainly to encourage explanations of why participants have answered the way they have.

The interviews will last 20-30mins and will be recorded using encrypted digital recording software. They will be conducted by the study co-ordinator. No potentially identifiable information will be recorded and participants will be advised not to divulge identifiable information prior to the interview. If this occurs inadvertently it will be deleted prior to transcription. These audio recordings will be given a unique identification number and then be transcribed into text documents using a paid professional transcription service within the UK. Once the transcription has been completed the recording will be deleted.

The transcribed data will be stored on a NHS server. It will be available for access to the study team by password protection and on request in an anonymised form by the University of Exeter sponsor if required for monitoring purposes. Once the study is complete it will be stored on the University of

Exeter Open Research repository for the period required for 5 years and securely deleted from the NHS server.

The transcribed data will be coded and then undergo thematic analysis using NVIVO software. Coding will be done by the principal investigator and a proportion of the data will be separately coded by the 2 senior members of the study team. Interim analysis will be conducted after each 5 patients and the interview schedule may undergo some change to explore in more detail areas of interest that emerge.

If groups are underrepresented in the interim analysis then there may be targeted recruitment to the underrepresented group. This may include the characteristics of patient age and presenting problem. All recruitment will be undertaken by the clinical team.

**Participants will be informed at the point of recruitment that if they proceed to complete an interview that they will be given a £25 high street store “thank you” voucher. After completion of the interview details will be taken to allow it to be posted to an address of their choice. These address details will be written directly onto an envelope and will not be stored.**

#### **Interviews with staff**

**Staff participants will be recruited by the study team including by attending regular team meeting events (see staff study flow diagram p.viii). Potential participants will be given an information sheet to read and prior to interview will be asked to sign a consent form. A mutually convenient time to meet will be arranged at the initial meeting or through later discussions. Face-to-face interviews will be conducted from mutually agreed locations that may include a private room on the SAU, researchers’ office or participants’ office. If any participants prefer a telephone call then this will be offered as an alternative and telephone consent will be collected in the same manner as that described for patient participants.**

**The interviews will all be conducted from the Royal Devon and Exeter hospital using an encrypted digital recording device, will last around 20-30mins and data will be handled securely in the same way as patient interviews. Staff will be informed that although their name will not be used in any quotes that other staff may be able to guess their identity by their job role. Staff participants will be offered the opportunity to look at the research manuscript if there are any potentially sensitive or identifiable quotes included where possible.**

**Participants will be informed at the point of recruitment that if they proceed to complete an interview that they will be given a £25 high street store “thank you” voucher. This will be given to them by the researcher after completion of the interview.**

## **6 STUDY SETTING**

This is a single centre study based at the Royal Devon and Exeter Hospital. This hospital has a frequently-accessed surgical assessment unit but has not previously undertaken any other studies of ambulatory emergency care. It can therefore be considered to be a “typical” unit for a hospital of this size and suitable for this study.

Potential patient participants will be approached by members of the clinical team after having their details screened from the existing admission list on the surgical assessment unit. They will be given a

brief description of the study and those that are interested are given an information sheet and the option to either give contact details (telephone number) immediately to the clinical team, or to contact the research team directly themselves. Those that give contact details will have these written on a paper form that will be stored securely in a locked drawer on the surgical assessment unit. They will later be collected by the study team and stored on an encrypted password-protected database that will be stored on an NHS computer in a locked research office.

The interview data will be collected on site at the Royal Devon and Exeter Hospital. The telephone interview with audio recordings will be carried out from a secure office on the NHS site. Audio files of the participant consent procedure and the interviews will be downloaded from the recording device onto a secure hard drive and will be allocated a unique participant ID number with the ID key kept in a separate location to pseudonymise the data. Prior to sending the data for transcription the interviews will be coded in a fully anonymised format to protect the data ready for transcription by a professional UK based transcription service. Once the transcription is complete the audio files will be securely destroyed by the transcription service and the researcher.

## 7 SAMPLE AND RECRUITMENT

### 7.1 Eligibility Criteria

#### 7.1.1 Inclusion criteria

**Patients** - Adult patients of any gender over the age of 18 undergoing emergency ambulatory care via the surgical assessment unit for a general surgical condition will be included. A good understanding of the English language will be required in order understand the information provided and undertake a telephone based consent and interview process.

**Staff – Staff employed in the SAU including consultants, junior doctors, senior nurses and other ward staff such as junior nurses, healthcare assistants and ward receptionists.**

#### 7.1.2 Exclusion criteria for patient participants

The following are exclusion criteria:

- Children under the age of 18
- Adults without capacity to consent as participants for the study
- Those who have primarily presented with a condition that is not within the remit of general surgeons
- Those who had their care continued as an inpatient immediately following their initial presentation.
- Unable to understand or speak English to the level required to understand the information sheet or conduct the interview

#### Exclusion criteria for staff participants:

- **Refusal or withdrawal of consent**
- **Staff who have not worked in ambulatory care (e.g. inpatient care experience only)**

## 7.2 Sampling

**Patients** - Sampling will occur any time the surgical assessment unit is open and receiving patients – generally between the hours of 08:00am-22:00pm and 7 days a week. It is possible that there will be targeted recruitment later in the study by the clinical team if certain groups are overrepresented using the random sampling technique.

**Staff** – We will aim to recruit 3-5 staff members from each of the following groups: consultants, junior doctors, senior nurses, ward support staff.

### 7.2.1 Size of sample

The sample size of 20 for patient participants has been estimated from other similar studies that use a similar technique of semi-structured interviews and thematic analysis. We believe this is a valid estimate as this is a single centre study looking at people attending the same unit with similar conditions. We will conduct interim analysis after each 5 patients to allow ongoing estimates of the number needed to reach thematic saturation.

We will aim to recruit 3-5 staff participants from each of the following staff groups: consultants, senior nurses, junior nurses, junior doctors and other ward staff including junior nurses, healthcare assistants and ward receptionists. This is considered to be a good subgroup size for this type of qualitative research. The overall size for the staff group is estimated to be 12-15 participants.

### 7.2.2 Sampling technique

Potential participants are identified from the admission list on the surgical assessment unit by the clinical team.

Patients will initially be approached at random but purposive sampling may be used later in the study if demographic groups e.g. by age are under-represented. This strategy has been used as we believe different groups may have different attitudes and difficulties with aspects of emergency ambulatory care. However, many patient characteristics are difficult to select for at the point of sampling so this will not be possible for most characteristics other than age.

Staff will be approached as a group at team meetings and be given the opportunity to register their interest with Expression of Interest forms to later be approached individually to arrange a time for interview. Regular updates on the progress of the study will be given to the ward team at existing daily briefings by the nurse-in-charge in conjunction with the researcher to allow those who had not previously heard about the study an opportunity to make contact for further information and to complete Expression of Interest forms.

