## 7.3 Recruitment

### 7.3.1 Patient sample identification

Potential participants will be identified by the clinical team. There exists an admissions list on the surgical assessment unit that has basic patient details (name, date of birth and hospital number) and presenting problem listed. This is regularly consulted by the clinical team as part of their clinical work. Eligible patients will be given basic information about the study by the clinical team at the point at which they are being discharged from their ambulatory stay on the surgical admissions unit. Patients interested in finding out more about the study will be given an information sheet and given the option of either leaving their telephone number for the study team to make contact or contacting the study team themselves using contact information given on the information sheet.

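### Does calling the patient sample random, when recruitment is by clinical-team approach and opt-in, call for a change to the protocol?

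*Protocol*

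**What the plan says.** Two sections of the protocol attach the word random to patient sampling. Section 7.2.2 states: "Patients will initially be approached at random but purposive sampling may be used later in the study". Section 7.2 allows for targeted recruitment later on "if certain groups are overrepresented using the random sampling technique".

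The recruitment steps are set out elsewhere:

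- Section 6 has patients "approached by members of the clinical team after having their details screened from the existing admission list", after which those interested have "the option to either give contact details (telephone number) immediately to the clinical team, or to contact the research team directly themselves".
- Section 7.3.1 says: "Eligible patients will be given basic information about the study by the clinical team at the point at which they are being discharged".
- Section 5 says: "Participants will be recruited to the study by the clinical team by means of short verbal explanation and the provision of an information sheet".

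On targeting, section 5 says: "If groups are underrepresented in the interim analysis then there may be targeted recruitment to the underrepresented group". It adds: "This may include the characteristics of patient age and presenting problem". Section 7.2.2 also speaks of groups that are under-represented, gives age as its example, and says that for most other characteristics selection at the point of sampling will not be feasible.

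**The concern.** To a statistician, random sampling means a selection mechanism with known probabilities, such as a random list, random time slots or a sampling fraction. None appears in the readable text. Section 7.3.1 reads as though eligible patients in general are told about the study, which would be a consecutive or convenience approach with self-selection. Staff who followed 7.3.1 literally and staff who followed 7.2.2 literally might act differently.

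The targeting text adds to the doubt. Section 7.2 is triggered by over-representation, sections 5 and 7.2.2 by under-representation. Section 5 names presenting problem beside age, whereas 7.2.2 seems to leave only age as workable.

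The stake would be how group findings are read. Section 4.2 aims to identify which groups engage well with ambulatory care and for whom it may be unsuitable, and section 2 expects clinicians to use this when choosing patients. A reader who took the 20 patients for a probability sample could give statements about groups more weight than a volunteer sample supports.

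**Working it through.** There is no power calculation or formula to reproduce. Section 7.2.1 takes the 20 patients from similar interview studies and reviews that number against thematic saturation. The check is therefore a comparison of the text, plus one count.

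**Is the random label contradicted?** The sections answer different questions.

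| Question | Section | Answer |
|---|---|---|
| When can sampling take place? | 7.2 | Whenever the unit is open |
| Who is approached first? | 7.2.2 | Patients at random; mechanism not stated |
| From what source, and by whom? | 6, 7.2.2, 7.3.1 | The admission list, by the clinical team |
| When are they told? | 7.3.1 | At discharge from the ambulatory stay |
| How do they enter? | 5, 6, 7.3.1 | They leave a number or make contact themselves |

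Every row can hold at once. Opt-in does not conflict with a random approach, because a patient approached at random still has to volunteer. The gap is an undescribed mechanism, or an everyday use of the word to mean without deliberate selection.

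**Are the targeting rules opposed?** With a fixed number of interviews, a group with more than its share leaves another with less. The two triggers therefore describe the same imbalance from either side, and the permitted action, targeted recruitment, is the same. On characteristics, 7.2.2 rules out most of those other than age, not all. Section 7.3.1 shows that the admission list carries date of birth and presenting problem, the two items needed to target as section 5 allows. So presenting problem remains usable.

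**When can targeting act?** With reviews after each 5 patients and 20 planned, 20 / 5 = 4 reviews, after patients 5, 10, 15 and 20. Of these, 4 − 1 = 3 come before a further planned interview. This assumes recruitment stops at 20, which section 7.2.1 treats as an estimate. The amendment history shows that patients were already taking part before version 2.0, so the number of reviews still to come is not known.

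**Does any result depend on random selection?** Section 3 specifies thematic analysis. The protocol plans no proportion, confidence interval, test or weighting. Section 6 calls the unit typical; nothing says that about the patients interviewed. The opt-in route is stated openly in sections 5, 6 and 7.3.1.

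**The case for a change.** The best case for a change is that 7.2 presents random sampling as a technique, not a casual phrase, and nothing readable supports it. Section 1 asks whether experience varies with age, social circumstances and attending condition, so doubt about targeting on presenting problem touches the study's purpose. The clinical team does all the recruiting, and unit staff are themselves a study population, which is a further reason to describe the approach exactly. The sponsor has already acted to widen the range of participants by adding a voucher in amendment 1. Rewording three sections would be cheap.

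Part of this stands. The label is imprecise, one word for the trigger would be tidier than two, and the report should say how patients were actually approached. But these are matters of description.

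The changes that would alter conduct are harder to justify. A fixed trigger, such as any age band or presenting-problem group with nobody yet interviewed, would turn permissive purposive sampling into something close to a quota, on which qualitative researchers reasonably differ. Checking representation against the admission list would also use the details of people who are not participants. The protocol describes that list as a clinical tool, and the study database in section 8.6 covers participants only.

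**Conclusion.** No change to the plan is needed. The word random is used loosely in 7.2 and 7.2.2, and the targeting text is worded unevenly across three sections, but no contradiction in rules is shown. Followed as written, the plan gives a volunteer sample, with scope to seek out under-represented groups by age or presenting problem at the 5-patient reviews. That is an ordinary and adequate basis for thematic analysis.

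The size of the issue is editorial: two sections carry a loose label and one differs from the others in its trigger word. No estimate or test is affected, and the protocol makes no claim of a representative patient sample that would need withdrawing. A sensible analyst will report the approach as it was carried out.

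This rests on two assumptions: that the report will not lean on the word random to generalise about groups, and that the patient flow chart, not reproduced in the copy read, does not contradict the text. If the chart does show a random step, the label is simply correct.
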